7.1.2 Questions regarding criteria

The subject will be asked questions to determine fulfillment of inclusion and exclusion criteria as specified in sections 5.1 and 5.2. Eligible subjects will be enrolled.

7.1.3 Baseline questions

Enrolled subjects will answer questions about demographics, including age, race, ethnicity, and sex, as well as questions about their relevant medical history.

7.2 Image collection

7.2.1 Skin locations

The skin to be imaged may be healthy or have suspected or known disease. The skin of the eyelid may not be imaged.

7.2.2 Preparation

The skin to be imaged will be cleaned using an alcohol swab to remove dirt and any other debris. The skin may be marked with a skin marker or targeting accessory. A small amount of pharmaceutical-grade mineral oil, alcohol-based hand sanitizer, ultrasound gel, or other pharmaceutical-grade immersion fluid may be applied to the skin. Subjects may be asked to remove any electronic wearables (e.g: smart watches, fitness tracker, hearing aid) etc. before we begin imaging.

7.2.3 Image and video collection

We may capture macroscopic images of the subject using a commercially available camera to capture the location and context of the skin to be imaged with the device. We may also image skin using a commercially available dermatoscope to accurately capture skin tone and other macroscopic skin features. Dermatoscope imaging may occur either before or after applying immersion fluid depending on the type of dermatoscope used. Imaging with the *VioTM* will begin after skin preparation. Each *VioTM* image and video requires only a few seconds to acquire. Macroscopic imaging, dermatoscope imaging, and *VioTM* imaging may occur in any order. Participants may volunteer for more than one imaging location (e.g., the cheek, the forearm, the hand) in a single session. Steps 7.2.2 and 7.2.3 may be repeated for different imaging locations.

7.2.4 Subject feedback

Subjects may be asked to provide verbal feedback about the procedures, the device, their experience with standard dermatology care, and/or their opinions of hypothetical situations of how the device could be used in the future.

7.3 Completion

The subject may choose to end his/her participation at any time by notifying the Investigator(s) or designee, who will immediately stop image collection. In order to minimize bias in the collection of study data, information already collected may be included in data analysis.

The successful completion of the procedures, or subject withdrawal or termination of procedures, will be documented at the end of the subject's participation. Subject participation may occur over multiple visits, as subjects are allowed to participate more than once.

Subjects may be compensated for their participation up to \$50 per session.

7.4 Photographs of subjects (optional procedure)

Images or partial images of subjects may be collected during the procedures listed here. These may be used to demonstrate the clinical ease of use of the technology. These images may be used in publications and scientific meetings. Any identifying features, e.g., faces of subjects, will be obscured in any published images.

7.6 Device Accountability and Traceability

All investigational devices will be stored at the investigational site in accordance with Good Clinical Practice (GCP) requirements and will be inaccessible to unauthorized personnel. Special storage conditions, if applicable, and a complete record of lot numbers and expiry dates can be found in the study file. Receipt, distribution, and destruction (if any) of the study device must be properly documented. Investigator(s) will be required to keep device accountability logs to ensure that devices are only used in properly consented subjects.

[figure not shown]

Figure 3. Schematic of procedures. The procedures outlined here are expected to typically take 1 hour, but no more than 3 hours.

8 Statistical procedures

8.1 Sample size determination

Although nonlinear imaging of human skin has been performed for years, little statistically meaningful data has been gathered to justify a robust sample size determination. A sample size of 120 was chosen to provide options for imaging skin of different demographics and minor technology modifications, although there are no strict requirements on enrollment of different groups for this protocol [2 (technology versions) \times 2 (sex; male, female) \times 5 (age; younger children, older children, young adults, middle aged adults, older adults) \times 5 (race/ethnicity; latino/a, black, Indian, Asian, white) = 100+(overhead)=120]. The sample size calculation for this study is justified because this study is purely observational.

8.2 Statistical methods

The primary analysis involves the quantification of imaging performance of the *VioTM* as a function of skin type, location (e.g., forearm, ear, nose), and health of skin. Because group sizes are small, statistical comparisons are unlikely to be significant. Still, data from this study will be important for planning statistically robust future studies. As a secondary aim, image performance will also be qualitatively evaluated by physicians trained in dermatopathology interpretation. Interim analyses are not planned.

8.3 Subject population(s) for analysis

All eligible subjects that are imaged will be included in the primary analysis according to the Aims outlined in Section 3. Non-primary analyses such as subject response to the procedure, occurrence of image artifacts, or typical reasons for screen failures may be reported for all subjects who consented to the study, or any defined subset of consented subjects.

9 Safety and adverse events

9.1 Definitions

Adverse event

An adverse event (AE) is any untoward medical occurrence (i.e., any unfavorable and unintended sign [including abnormal laboratory findings], symptom, or disease) in a clinical investigation subject after providing written informed consent for participation in the study. Therefore, an AE may or may not be temporally or causally associated with the use of the device.

A surgical procedure that was planned prior to the start of the study by any physician treating the subject should not be recorded as an AE.

In the following differentiation between medical history and AEs, the term “condition” may include abnormal physical examination findings, symptoms, diseases, laboratory findings, and electrocardiogram findings.

- Conditions that started before signing of informed consent and for which no symptoms or treatment are present until signing of informed consent are recorded as medical history (e.g., seasonal allergy without acute complaints).

- Conditions that started before signing of informed consent and for which symptoms or treatment are present after signing of informed consent, at *unchanged intensity*, are recorded as medical history (e.g., allergic pollinosis).
- Conditions that started or deteriorated after signing of the ICF will be documented as AEs.

Adverse device effect

An adverse device effect (ADE) is an AE related to the use of the device, including AEs resulting from insufficient or inadequate instructions for use, installation or operation, or any malfunction of the investigational medical device, use error or from intentional misuse of the medical device. The term is synonymous with device-related adverse event.

Device deficiency

A device deficiency is an inadequacy of device related to its identity, quality, durability, reliability, safety, or performance, such as malfunction, misuse, or use error and inadequate labeling.

Device failure

A device failure is a failure of the device to perform or function as intended, including any deviations from the performance specifications, or intended use.

Device malfunction

A device malfunction is a failure of the device to meet its performance specifications or otherwise perform as intended when used in accordance with the IFU (User Manual).

Device misuse

A device misuse occurs when the Investigator or designee uses the device in a manner that is contradictory to the IFU (User Manual). A device misuse will not be considered a malfunction.

Device-related adverse event

A device-related adverse event is any AE for which a causal relationship between the device and the AE is at least a reasonable possibility (i.e., the relationship cannot be excluded). The term is synonymous with adverse device effect (ADE).

Near incident

A near incident is any malfunction or deterioration in the characteristics and/or performance of the device (an ADE) which might have led to death or serious deterioration in health. The incident occurred and is such that if it occurred again, it might lead to death or serious deterioration in health.

Serious adverse device effect

An ADE that results in any of the consequences of a SAE. The term serious adverse device effect (SADE) is synonymous with “incident”.

Serious adverse event (SAE)

Any untoward medical occurrence that, at any dose, meets any of the following criteria (a—g):

- a. Results in death.
- b. Is life-threatening.

The term 'life-threatening' in the definition refers to an event in which the subject was at risk of death at the time of the event, it does not refer to an event which hypothetically might have caused death if it were more severe.

- c. Requires inpatient hospitalization or prolongation of existing hospitalization.

A hospitalization or prolongation of hospitalization will not be regarded as an SAE if at least one of the following exceptions is met:

- o The admission results in a hospital stay of less than 12 hours.
 - o The admission is pre-planned
(i.e., elective or scheduled surgery arranged prior to the start of the study).
 - o The admission is not associated with an AE
(e.g., social hospitalization for purposes of respite care).

However, it should be noted that invasive treatment during any hospitalization may fulfill the criterion of 'medically important' and as such may be reportable as an SAE dependent on clinical judgment. In addition, where local regulatory authorities specifically require a more stringent definition, the local regulation takes precedence.

- d. Results in persistent or significant disability / incapacity.

Disability means a substantial disruption of a person's ability to conduct normal life's functions.

- e. Is a congenital anomaly / birth defect.

- f. Results in fetal distress, fetal death or a congenital abnormality or birth defect.

- g. Is another medically important serious event as judged by the Investigator.

Unanticipated adverse device effect

An unanticipated adverse device effect (UADE) is any SADE on health or safety, or any life-threatening problem or death caused by, or associated with, a device, if that effect, problem, or death was not previously identified in nature, severity, or degree of incidence in the investigational plan or application or any other unanticipated serious problem associated with a device that relates to the rights, safety, or welfare of subjects.

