9.4 Stopping rules

Safety findings may trigger a temporary suspension of enrollment until an *ad hoc* safety review is conducted to determine whether the study should continue per protocol, proceed with caution, be further investigated, be discontinued, or be modified then proceed.

A safety review may be triggered by the occurrence of a UADE, or the occurrence or increased frequency of any situation the Sponsor-Investigator deems to be a trigger. Any findings shall be reported to the designated employees of Enspectra Health, who will then conduct a safety review and determine what steps will be taken.

The study may be discontinued at any time by the IRB, the FDA, or other government agencies as part of their duties to ensure that research participants are protected.

Participation of individual subjects may be terminated for multiple reasons, including failure to follow the Investigator's or designee's instructions, revelation of inaccurate information provided

during the screening process, safety reasons, subject is experiencing clear stress or pain (but the subject does not want to withdraw), or any scenario in which the Investigator judges it to be in the subject's best interest to terminate that subject's participation.

9.5 *Medical monitoring*

A medical monitor will be appointed for the study. The medical monitor will be a physician who is not involved in conducting the study and who has no or minimal conflict of interest. The medical monitor is responsible for ongoing monitoring of adverse event reports to identify safety concerns quickly. The medical monitor may also serve as a resource to the Sponsor-Investigator for advice about management of adverse events.

10 Data handling and record keeping

10.1 *Confidentiality*

All records identifying the subject will be kept confidential and, to the extent permitted by the applicable laws and/or regulations, will not be made publicly available.

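### The hospitalization exceptions in the SAE definition, applied literally, cancel an AE-caused prolongation of 12 hours or more whenever the original admission was pre-planned or not AE-related

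*Combined protocol and SAP*

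**What the plan says.** In 9.1 Definitions, criterion c of the serious adverse event definition reads "Requires inpatient hospitalization or prolongation of existing hospitalization". The exception sentence that follows takes in both limbs: "A hospitalization or prolongation of hospitalization will not be regarded as an SAE if at least one of the following exceptions is met". The three exceptions are:

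- "The admission results in a hospital stay of less than 12 hours"
- "The admission is pre-planned", explained as "elective or scheduled surgery arranged prior to the start of the study"
- "The admission is not associated with an AE", with respite care as the example

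The section then softens the exceptions in two ways. It states: "invasive treatment during any hospitalization may fulfill the criterion of 'medically important' and as such may be reportable as an SAE dependent on clinical judgment". It also lets a more stringent local regulation override the definition. Criterion g separately admits any event that the Investigator judges medically important and serious.

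Section 9.2.1 requires the seriousness of every AE to be decided by the 9.1 criteria. Also in 9.1, a SADE is a device-related AE with an SAE consequence, and a UADE includes any unanticipated SADE. Section 9.4 says "A safety review may be triggered by the occurrence of a UADE", and goes on to allow a review for whatever else the Sponsor-Investigator considers a trigger.

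**The concern.** Criterion c names prolongation as a ground for seriousness in its own right. The exceptions name prolongation too, but decide it by facts about the original admission. A complication that keeps a subject in hospital is thus classified by why the subject came in, not by why the subject stayed.

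The situation can arise here. The study may image diseased skin, including basal cell carcinoma, and takes physician referrals, so some subjects may have surgery already arranged. Suppose such a subject develops an infection at the imaged site and is kept in for extra days. The admission is pre-planned, so criterion c does not count the prolongation.

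At stake is the serious label and what follows from it: SADE classification, the notification of serious events to the IRB and authorities under 9.2.3, and one route to UADE. No planned efficacy or performance analysis is affected. Section 8 specifies no analysis of serious-event counts, and the study sets no quantitative endpoints.

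**Working it through.** There is no stated figure to reproduce. The check is a trace of the rule as logic.

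**Inputs (all from 9.1).** H = hospitalization; P = prolongation of an existing stay; E1 = stay under 12 hours; E2 = admission pre-planned; E3 = admission not associated with an AE. One exception is enough, so they combine by OR.

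**Rule.** Serious under c = (H or P) and not (E1 or E2 or E3).

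**Trace.** Take an AE that prolongs a stay of 12 hours or more and meets no other criterion. P is true and E1 is false. The combination of a pre-planned and an AE-related admission is left out: surgery arranged before the study cannot result from an AE, which by definition begins or worsens after consent. Three admission types remain:

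| Original admission | E2 | E3 | Prolongation serious under c? |
|---|---|---|---|
| Pre-planned | true | true | No |
| Unplanned, not AE-related | false | true | No |
| Unplanned, AE-related | false | false | Yes |

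The prolongation limb works in 1 of 3 types, the one in which the admission was itself already due to an AE. This counts logical cases, not expected events. Stays under 12 hours fail through E1, which is a separate rule and not the complaint.

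**Carry-through if the AE is device-related.** In the first two rows there is no SAE consequence under c, hence no SADE under c and no UADE through its SADE limb.

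**What stays open in those rows.**

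- SAE status: criterion g (judgment); the invasive-treatment sentence (worded with *may*, and dependent on clinical judgment); stricter local regulation (only where it exists). Criteria a, b and d to f are unaffected.
- UADE status: 9.1 has a further limb for other unanticipated serious problems associated with the device, which does not pass through SADE.
- Visibility: 9.2.2 collects all AEs, related or not, to one week after participation ends and follows them until they subside or stabilize. Under 9.5 the medical monitor reviews adverse event reports generally.
- Safety review: 9.4 lets the Sponsor-Investigator trigger one for reasons other than a UADE.

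**The case against.** The best defence is that the sentence means less than it says. An SAE is an untoward medical occurrence, and 9.1 elsewhere keeps previously planned surgery from being recorded as an AE. On that reading the exceptions remove only the planned or social stay itself, not a new complication. That is very likely the intent, but the wording does not deliver it. The exception sentence expressly names prolongation, and the examples, surgery arranged beforehand and respite care, can only describe the original admission. Since 9.2.1 makes the 9.1 criteria binding, an assessor who follows the text reaches the wrong answer.

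The rest of the defence concerns consequences, and most of it stands. A reader might infer any of the following, and the documents do not support them:

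- *That a prolongation managed without invasive treatment has no way back to serious status.* Criterion g is not limited to invasive treatment, and stricter local regulation takes precedence.
- *That the event could no longer be a UADE or prompt a safety review.* UADE has its independent limb, and the 9.4 trigger extends beyond UADEs. Even for a UADE the review is permitted, not required.
- *That the infection example shows a lost UADE.* Infection is among the risks in 1.4.2, which 9.2.4 names as the list of expected events. Unless its severity or incidence was unanticipated, it would not be a UADE even if correctly classed as serious. The example shows loss of SAE status and, if the infection is device-related, SADE status only.
- *That an expected number of such events can be stated.* No hospitalization rate is given. Subjects may also attend more than once, so a single 7-day window per subject is not a safe basis for one.

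What survives is narrower: an objective criterion is switched off in two of three cases, and apart from local regulation the routes that replace it rest largely on judgment.

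**Conclusion.** The definition is wrong as written, and the point is minor. Criterion c and its exceptions conflict for an AE that prolongs a stay of 12 hours or more after a pre-planned or non-AE admission. The loss is of SAE status under that one criterion and, only where the AE is device-related, of SADE status and the SADE route to UADE. The event itself is not lost from the safety data.

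Frequency cannot be computed from the documents. That it is rare is a judgment, resting on a non-invasive procedure, up to 120 subjects and AE collection that ends a week after participation. The conclusion also assumes that assessors apply the text literally and that no stricter local rule already overrides it.

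**What to change.** At the next amendment, in 9.1:

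1. Leave the 12-hour exception as it stands. Nothing here argues for changing it.
2. Confine the pre-planned and not-AE-associated exceptions to the admission itself.
3. Add a sentence such as: *Prolongation of a pre-planned or non-AE admission because of an AE is not covered by these two exceptions and, unless the 12-hour exception applies, meets criterion c.*

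The cost is a short wording change with no added data collection. The downside is that a rare extra event is counted and reported as serious. Planned operations would not be drawn in, because 9.1 already keeps them from being recorded as AEs.

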9.2 Recording and reporting of adverse events

9.2.1 Classifications for adverse event assessment

All AEs will be assessed and documented by the Sponsor-Investigator according to the categories detailed below:

a) Seriousness: For each AE, the seriousness must be determined according to the criteria given in Section 9.1 (*Definitions*).

b) Intensity: The intensity of an AE is classified according to the following categories:

- Mild
- Moderate

- Severe

c) Causal relationship: The assessment of the causal relationship between an AE and the device or procedure is a clinical decision based on all available information at the time of the completion of the CRF. The assessment is based on the question whether there was a “reasonable causal relationship” to the procedure and/or device.

- Possible responses to causal relationship are “yes”, “possibly”, or “no”.
- An assessment of “no” would include (1) the existence of a clear alternative explanation (e.g., the subject develops a local infection from an unrelated laceration) or (2) non-plausibility (e.g., the subject is struck by an automobile when there is no indication that the device caused disorientation that may have caused the event).
- An assessment of “possibly” indicates that there is a reasonable suspicion that the AE is associated with the procedure and/or device, but not definitively so.
- An assessment of “yes” indicates that the AE is very likely associated with the procedure and/or device.
- Important factors to be considered in assessing the relationship of the AE to the device or procedure include (1) the temporal sequence from the procedure—the event should occur after the procedure is initiated, (2) Underlying, concomitant, intercurrent diseases—each event should be evaluated in the context of the natural history and course of the procedure and any other medical conditions the subject may have, and (3) concomitant medications or procedures—any drugs the subject is taking or the additional procedures the subject receives should be examined to determine whether any of them may be suspected to cause the event in question.
- If the AE is assessed as related, it must be determined if the AE was associated with the device itself or with the procedure.

Causal relationship to other protocol-required procedure(s): The assessment of a possible causal relationship between the AE and other protocol-required procedure(s) is based on the question of whether there was a “reasonable causal relationship” to any protocol-required procedure(s). This category does not apply to AEs that are assessed by the Sponsor-Investigator as being related to the device itself or to the actual use of the device. Possible answers are “yes”, “possibly”, or “no.”

d) Outcome: The outcome of the AE is to be documented as follows:

- Recovered/resolved
- Recovering/resolving
- Recovered/resolved with sequelae
- Not recovered/not resolved
- Fatal
- Unknown

